## Statistical Analysis Plan

### 1.5 Randomization

[REDACTED]

### 1.6 Blinding

[REDACTED]

## 2.0 ANALYSIS CONSIDERATIONS

### 2.1 Analysis Populations

[REDACTED]  
[REDACTED]  
[REDACTED]

#### 2.1.1 [REDACTED]

[REDACTED]  
[REDACTED]

#### 2.1.2 [REDACTED]

[REDACTED]  
[REDACTED]

#### [REDACTED] [REDACTED]

[REDACTED]  
[REDACTED]  
[REDACTED]

### 2.2 Statistical Methods

Descriptive analysis will be performed to summarize baseline, procedural, and safety event data. Depending on the type of data (e.g., continuous or categorical), appropriate statistical methods described in the section below will be used.

#### 2.2.1 Descriptive Statistics for Continuous Variables

For continuous variables, such as age, results will be summarized with the numbers of observations, means, and standard deviations, and if specified in the table mockups, with quartiles, minimums, maximums, and 95% confidence intervals for the means. When performing subgroup analyses, differences between the two groups, where specified, will be summarized with the differences of the two means, and 95% confidence intervals for the difference between the means. These calculations will be done under the assumption that data for the two groups are independent and approximately normally distributed. The confidence interval for the difference of two means will be calculated under the assumption of unequal variances. If the asymptotic assumptions fail, then nonparametric summary statistics (medians, 25th and 75th percentile) may be displayed as an alternative (Appendix F).

## Statistical Analysis Plan

### 2.2.2 Descriptive Statistics for Categorical Variables

For binary variables (e.g. gender, diabetic status, etc.), results will be summarized with patient counts and percentages/rates with exact 95% Clopper-Pearson confidence intervals. When performing subgroup analyses, differences between the two groups, when specified, will be summarized with the difference in percent and the Newcombe score 95% confidence interval for the difference of two percentages (Appendix G).

### 2.2.3 Categorical variable effect analysis

The effect of categorical variable on binary outcome (i.e. primary safety endpoint, primary effectiveness endpoint) will be analyzed using a logistic regression model.

Summary tables for each category in the categorical variable will include odds ratios and confidence intervals.

## 2.3 Endpoint Analysis

### 2.3.1 Primary Endpoint(s)

#### 2.3.1.1 Primary Safety Endpoint

The primary safety endpoint is the rate of device and/or procedure-related serious adverse events with onset within 7 days of any ablation procedure (initial or repeat procedure)

The primary safety endpoint hypothesis is stated as follows:

[REDACTED]  
[REDACTED]

[REDACTED]  
[REDACTED]  
[REDACTED]

[REDACTED]  
[REDACTED]

[REDACTED]

- [REDACTED]
- [REDACTED]
- [REDACTED]
- [REDACTED]
- [REDACTED]
- [REDACTED]
- [REDACTED]
- [REDACTED]
- [REDACTED]
- [REDACTED]
- [REDACTED]
- [REDACTED]
- [REDACTED]
- [REDACTED]
- [REDACTED]

[REDACTED]

[REDACTED]  
[REDACTED]

## Statistical Analysis Plan

[REDACTED]

[REDACTED]

[REDACTED]

[REDACTED]

### 2.3.1.2 Primary Effectiveness Endpoint

The primary effectiveness endpoint for this clinical trial is freedom from AF/AFL/AT episodes of >30 seconds duration that is documented by an ECG (12-lead or TTM) or 24-hour Holter after the initial catheter ablation procedure through 15 months of follow-up.

The hypothesis is formally expressed as:

[REDACTED]

[REDACTED]

- [REDACTED]
- [REDACTED]
- [REDACTED]
- [REDACTED]
- [REDACTED]
- [REDACTED]
- [REDACTED]

[REDACTED]

[REDACTED]

[REDACTED]

## Statistical Analysis Plan

[REDACTED]

[REDACTED]

### 2.3.2 Secondary Endpoints

#### 2.3.2.1 Achievement of Acute Procedural Success

The secondary endpoint is the proportion of subjects who achieve acute procedural success at the end of the initial procedure; where acute procedural success is defined as confirmation of entrance block in all pulmonary veins.

The hypothesis is stated as follows:

[REDACTED]

[REDACTED]

#### 2.3.2.2 Chronic Success Off Antiarrhythmic Drugs

This secondary endpoint is chronic success off antiarrhythmic drug; where chronic success is defined as freedom from documented AF/AFL/AT recurrence (episodes >30 seconds) during the 9-month period following the blanking and therapy consolidation periods.

The hypothesis is stated as follows:

[REDACTED]

[REDACTED]

## Statistical Analysis Plan

[REDACTED]

### 2.3.2.3 Asymptomatic and Symptomatic Single Procedure Success

This secondary endpoint is asymptomatic or symptomatic single procedure success; where single procedure success is defined as freedom from all documented AF/AFL/AT recurrence of >30 seconds.

The hypothesis is stated as follows:

[REDACTED]

[REDACTED]

### 2.4 Sample Size Calculations

[REDACTED]

[figure not shown]
#### 2.4.1 [REDACTED]

[REDACTED]

#### 2.4.2 [REDACTED]

[REDACTED]

## Statistical Analysis Plan

### 2.5 Interim Analysis

[Redacted]

### 2.6 Timing of Analysis

The primary endpoint analysis will be performed and the pre-market approval (PMA) clinical report will be submitted after the last subject has completed the 15-month follow-up or passed the end of their 15-month visit window.

### 2.7 Study/Trial Success

[Redacted]

### 2.8 Subgroups for Analysis

Subgroup analyses will be performed to examine the consistency of results for the primary safety and effectiveness endpoints. [Redacted]

[Redacted]

### 2.9 Handling of Missing Data

[Redacted]

[Redacted]

## Statistical Analysis Plan

### 2.10 Poolability Analysis

[Redacted]

[Redacted]

[Redacted]

### 2.11 Multiplicity Issues

[Redacted]

[Redacted]

### 2.12 Adjustments for Covariates

Unless otherwise specified, no adjustments for covariates will be made for any of the variables in the analyses.

### 2.13 Sensitivity Analysis

#### 2.13.1 Missing Data

[Redacted]

- [Redacted]

[Redacted]

- [Redacted]

[Redacted]

- [Redacted]

[Redacted]

[Redacted]

[Redacted]

## Statistical Analysis Plan

### 2.13.2 Protocol Compliance

### 2.13.3 Covid-19

To assess the impact of Covid-19 on primary safety endpoint and primary effectiveness endpoint, the following sensitivity analyses will be performed on the PTE population:

- Primary safety endpoint

- Primary effectiveness endpoint

## 3.0 ADDITIONAL INFORMATION

### 3.1 Baseline and Demographic Characteristics

The following baseline and demographic variables, including but not limited to: gender, age, ethnicity, race, cardiac disease history, arrhythmia history, etc. will be summarized for subjects in PTE analysis population.

### 3.2 Adverse Events

Safety surveillance and reporting starts as soon as the patient is enrolled in the clinical investigation. Adverse event data, including deaths, will be collected starting at the time of consent and throughout the 15-month follow-up period and will be reported to the Sponsor on the Adverse Event CRF. Safety surveillance and reporting will continue until the last follow-up visit has been performed, the subject is deceased, the subject concludes participation in the clinical investigation or the subject withdraws from the clinical investigation.

For the purposes of this clinical investigation, the following adverse events will be reported:

- Adverse events that are adjudicated by the investigator as being related to either the ablation catheter or the ablation procedure
- Serious adverse events, regardless of relatedness to the procedure and/or the ablation catheter

Recurrence of AF, AFL, or AT are not considered reportable adverse events unless they occur in severity, frequency, or other manner that is significantly worse than the subject's baseline condition. Recurrence of AF, AFL, or AT will affect the primary effectiveness endpoint and should be reported on the Follow-Up Visit CRF.

Additionally, urinary tract infections (UTIs) that occur after a procedure and do not require a Foley catheter will not be considered adverse events. UTIs that require a Foley catheter will be reported as AEs if related to the procedure or meet serious criteria.

## Statistical Analysis Plan

Unchanged, chronic, non-worsening or pre-existing conditions are not AEs and should not be reported.

All adverse events (AEs), adverse device effects (ADEs), serious adverse events (SAEs), serious adverse device effects (SADEs), and unanticipated adverse device effect (UADEs) will be summarized for all subjects enrolled in this trial in terms of the number of events and the percentage of subjects with events.

CEC adjudicated results will be used for analysis. The investigator adjudicated results will be summarized in the final report.

AEs from the FAS population will be summarized separately for subjects who were consented but did not have an investigational catheter inserted into their vasculature from those subjects who are in the PTE population.

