4.3 Additional Data

Additional data to be collected in this clinical investigation are described and will be reported using summary statistics. No hypothesis tests will be performed.

- 1) Procedure- and/or ablation catheter-related adverse events throughout the 15-month follow-up period
 - 2) Success (defined as freedom from >30 second documented episodes of AF/AFL/AT recurrence) without Class I or III AAD dose increase from the historic maximum ineffective dose (prior to the ablation procedure) or initiation of a new Class I or III AAD for arrhythmia recurrence after the blanking and therapy consolidation periods.
- 

- 3) Proportion of subjects who achieve 15-month symptomatic single procedure success (defined as freedom from >30 second documented symptomatic episodes of AF/AFL/AT recurrence after the blanking and therapy consolidation periods).
- 4) Cardiovascular-related health care utilization through 15-months after the initial procedure.
- 5) Procedure data, including but not limited to, ablation data, mapping data, and usage of Automark.
- 6) Proportion of cases achieving $\geq 90\%$ lesions with $\geq 10g$ of contact force.
- 7) Evaluation of procedure data to determine target lesion index (LSI) value(s) as assessed by AF/AFL/AT recurrence.
- 8) Changes in EQ-5D-5L and AFEQT scores from baseline to follow up at 3, 6, 12, and 15-months after the initial procedure.

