5.5 Subject Withdrawal

Each enrolled subject shall remain in the clinical investigation until completion of the required follow-up period. However, a subject's participation in any clinical investigation is voluntary and the subject has the right to withdraw at any time without penalty or loss of benefit.

Abbott must be notified of the reason(s) for subject discontinuation. The site will provide this information to Abbott as documented on the appropriate CRF. Investigators must also report this to their respective IRB/EC as defined by their institution's procedure(s).

No additional follow-up will be required or data recorded from subjects once they are withdrawn from the clinical investigation. If a subject withdraws from the investigation due to problems related to the safety or performance of the device under investigation, they will be followed by their regular physician per their standard of care.

If for any reason, the subject has the TactiCath SE inserted into their vasculature, but no ablation is performed and the subject will not be rescheduled to receive another ablation procedure, the subject will be followed for 30-days to assess safety and then exited from the trial.

In the event that a subject does elect to withdraw from the trial, the site should make attempts to schedule the subject for a final visit. At this final follow-up visit, the subject will undergo assessments as outlined for an unscheduled visit (**Section 6.6.2**), if the visit does not coincide with a scheduled follow-up visit.

Withdrawn subjects count towards the total enrollment at the site and will not be replaced by enrolling additional subjects.

Lost-to-Follow-up

If the subject misses two consecutive scheduled follow-up time points and the attempts at contacting the subject (detailed below) are unsuccessful, then the subject is considered lost-to-follow-up. Site personnel shall make all reasonable efforts to locate and communicate with the subject and document their efforts, including the following, for each time an attempt was made to contact the subject:

- A minimum of two telephone calls on different days over the specified follow-up windows to contact the subject should be recorded in the source documentation, including date, time and initials of site personnel trying to make contact.
- If these attempts are unsuccessful, a letter should be sent via registered mail to the subject.

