8.2.2.3 Secondary Endpoint - Asymptomatic and Symptomatic Single Procedure Success

The hypothesis is stated as follows:

[REDACTED]

[REDACTED]

[REDACTED]

[REDACTED]

[REDACTED]

[REDACTED]

[REDACTED]

[REDACTED]

power to reject the null hypothesis with a performance goal of 16.8% and an attrition rate of 20%, is 224

[REDACTED]

[REDACTED]

[REDACTED]

[REDACTED]

[REDACTED]

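### Adverse event percentages over 15 months count withdrawn subjects as event-free, so they may understate late harms outside the primary safety endpoint

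*SAP*

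**What the plan says.** - **Summary method.** SAP 3.2 says that AEs, ADEs, SAEs, SADEs and UADEs "will be summarized for all subjects enrolled in this trial in terms of the number of events and the percentage of subjects with events". Subjects who consented but had no catheter inserted are tabulated apart from the PTE population.
- **Collection window.** The same section says that event data "will be collected starting at the time of consent and throughout the 15-month follow-up period". Surveillance ends at the last visit, at death, or when "the subject concludes participation in the clinical investigation or the subject withdraws from the clinical investigation".
- **After withdrawal.** Protocol 5.5: "No additional follow-up will be required or data recorded from subjects once they are withdrawn from the clinical investigation". It adds: "Withdrawn subjects count towards the total enrollment at the site and will not be replaced by enrolling additional subjects". Protocol 5.5 and 6.3 also exit subjects at 30 days if the catheter was inserted, no ablation was done and none is rescheduled.
- **Attrition.** The partly redacted sample-size text (Protocol 8.3 in the contents list) leaves one legible line: "power to reject the null hypothesis with a performance goal of 16.8% and an attrition rate of 20%, is 224".
- **Status of the tables.** Protocol 4.3 lists "Procedure- and/or ablation catheter-related adverse events throughout the 15-month follow-up period" as its first item of additional data, which "will be reported using summary statistics. No hypothesis tests will be performed".
- **Late harms in the primary safety endpoint.** Most components count only with onset within 7 days of a procedure. Atrioesophageal fistula, cardiac tamponade/perforation and pulmonary vein stenosis are evaluated through 15 months (Protocol 4.1.1, SAP 1.4.1).

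**The concern.** A percentage of all subjects with an event estimates the 15-month risk only if everyone is watched for 15 months. Here observation ends at withdrawal, but the wording of SAP 3.2 keeps the subject in the denominator. Someone who leaves at month 4 is treated as having no stroke or other SAE up to month 15. Events that are not seen can only lower the figure, so the error runs in one direction and grows with the lateness of the event.

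A stroke, TIA, thromboembolism or death at month 4 lies outside the 7-day window of the primary safety endpoint. In the readable text, the AE tables are where such an event would be reported. Because Protocol 4.3 frames these events over the whole 15 months, a reader may well take the percentages as 15-month risks.

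**Working it through.** **The plan's own figure.** An allowance of 20% on 179 evaluable subjects gives 179 / (1 − 0.20) = 223.75, rounded up to 224. So 224 is consistent with 179 evaluable subjects. The step that leads to 179 cannot be reproduced, because alpha, power and the expected event rate are not public.

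**Inputs.** From the documents: follow-up of 450 days (15-month visit, Protocol 6.6), N = 224, attrition d = 20%. Assumed, because the documents do not give them: true 15-month risks R of 2 to 10%, the timing of events and withdrawals, and withdrawal unrelated to harm.

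**Formula.** The expected crude proportion is the integral over 450 days of the event density f(t) times G(t), the probability of still being in the study. If withdrawals are uniform, G(t) = 1 − d·t/450, and

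crude / true = 1 − d × (mean event day) / 450.

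| Events spread evenly over | Mean event day | Ratio at d = 20% |
|---|---|---|
| Days 0–7 | 3.5 | 1 − 0.20 × 3.5/450 = 0.998 |
| Days 0–450 | 225 | 1 − 0.20 × 225/450 = 0.900 |
| Days 30–450 | 240 | 1 − 0.20 × 240/450 = 0.893 |
| Days 90–450 | 270 | 1 − 0.20 × 270/450 = 0.880 |

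- **Other withdrawal timing at 20%.** All losses at the end: 1.00. All at the start: 0.80. The relative shortfall is therefore 0 to 20%.
- **Lower attrition, events on days 30–450.** At 10%: 1 − 0.10 × 240/450 = 0.947. At 5%: 0.973.
- **Absolute scale, d = 20% uniform, events on days 30–450.** A true 2% shows as 1.79%, 5% as 4.47% and 10% as 8.93%.

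**Check with constant rates.** With event hazard l and dropout hazard m per month, crude = l/(l+m) × (1 − exp(−15(l+m))). For R = 10% and d = 20%, 15l = 0.1054 and 15m = 0.2231. This gives 0.1054/0.3285 × (1 − exp(−0.3285)) = 8.98%. If the events fall only in months 6 to 15, the result is 8.57%. At 10% attrition the two figures are 9.50% and 9.30%.

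**Check by simulation.** There were 20,000 runs with N = 224, R = 5%, events on days 30–450 and 20% uniform withdrawal. The mean crude percentage was 4.48% and the mean Kaplan-Meier estimate 5.01%. The gap of about 0.53 points is 11% relative, or about 1.2 subjects of 224. No competing deaths were simulated, so Aalen-Johansen and Kaplan-Meier coincide here. The standard deviation was 1.38 points for the crude figure and 1.54 for Kaplan-Meier.

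**Scale of sampling error.** The exact 95% interval for 11/224 (4.9%) is 2.5% to 8.6%.

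**The case against.** The strongest reply is that these are descriptive tables. Protocol 4.3 plans no tests on them, and no passage calls the percentages a 15-month risk or says that they carry the safety claim to the regulator. That is right, and it limits the point to how the figures may be read.

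Three stronger readings are tempting, and the documents do not support them:

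- **That late pulmonary vein stenosis, atrioesophageal fistula or tamponade is understated, or that the primary safety result is biased.** These harms sit in the primary safety endpoint through 15 months. Its analysis (SAP 2.3.1.1), missing-data handling (2.9) and missing-data sensitivity analyses (2.13.1) are redacted. Protocol 3.2 promises sensitivity analyses on missing data. A suitable method cannot be called absent.
- **That a fifth of treated subjects will be lost.** The 20% is a sample-size allowance whose definition and timing are not visible. It may include subjects who never had a catheter inserted, and SAP 3.2 already tabulates those separately.
- **That the plan reports a wrong 15-month risk.** It reports a percentage and does not say what that percentage estimates.

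There is also mitigation. Sites attempt a final visit at withdrawal and must document attempts at contact (Protocol 5.5). Early-termination reasons are summarised (SAP 3.3). SAP 2.2 applies its descriptive methods to safety data, with exact intervals for binary variables. These help a reader see incomplete follow-up, but they do not correct for it: an exact interval also treats each subject as fully observed.

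Finally, the shift is well inside sampling error, and in the simulation the corrected estimate was somewhat more variable. Both are true. What stands is that the error has a known direction and can be removed at little cost if withdrawal is unrelated to harm.

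**Conclusion.** The point holds as a modest improvement to reporting. For harms after day 7 outside the primary safety endpoint, the SAP 3.2 percentages may understate 15-month risk. At 20% attrition the relative shortfall is 0 to 20%, about 10 to 12% under uniform withdrawal; at 10% attrition it is about 5%. Events in the first week are almost unaffected unless subjects leave within days of the procedure.

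This rests on reading SAP 3.2 as a fixed denominator that keeps withdrawn subjects, which is its plain sense, and on the assumed risks and timings above. The downward direction follows from the fixed denominator alone; the size does not. If subjects withdraw because of harm, the shortfall could be larger, and a censoring-based estimate would correct only part of it. No trial success criterion in the readable text depends on these tables.

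**What to change.** Keep the counts and percentages in SAP 3.2 and add one table for the PTE population:

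- **Estimator.** Aalen-Johansen cumulative incidence of a first device- or procedure-related AE, SAE and SADE, with time counted from the initial procedure. For non-fatal events, treat death as a competing event. Plain Kaplan-Meier would censor deaths and overstate the incidence.
- **Censoring.** At last contact. Under Protocol 5.5 a subject counts as lost only after two consecutive missed time points. Someone last reached at month 3 may therefore not be declared lost until after the 12-month contact, so the exit date can overstate observed time. Subjects exited at 30 days without ablation are censored at that contact.
- **Display.** 95% intervals and numbers at risk at 7 days and 3, 6, 12 and 15 months.
- **Use.** Quote these estimates, not the crude percentages, wherever a 15-month rate is stated, and note that they assume non-informative withdrawal.

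The cost is a few lines in SAP 3.2 and one table from event, visit and exit dates that the trial should already hold. Late-event rates would look slightly less favourable, with somewhat wider intervals. No endpoint, sample size or clinical rule changes.

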### 3.3 Subject Early Termination

Subject early termination reasons including deaths, withdrawals, and lost-to-follow-up and will be summarized from the time the subject meets eligibility criteria (after consent) throughout the 15-month trial follow-up period.

### 3.4 Protocol Deviation

Protocol deviations will be summarized by deviation categories for subjects in whom a protocol deviation was reported.

## 4.0 DOCUMENTATION AND OTHER CONSIDERATIONS

All analyses will be performed using SAS® for Windows, version 9.2 or higher.

## 5.0 ACRONYMS AND ABBREVIATIONS

Acronym or Abbreviation	Complete Phrase or Definition
AF	Atrial fibrillation
AFL	Atrial flutter
AT	Atrial tachycardia
AE	Adverse Event
ADE	Adverse device effect
AAD	Antiarrhythmic drug
APHRS	Asian Pacific Heart Rhythm Society
AFEQT	Atrial fibrillation effect on Quality-of-life
CEC	Clinical Events Committee
CIP	Clinical Investigation Plan
CRF	case report form
CVA	Cerebrovascular accident
ECG	Electrocardiography
EHRA	European Heart Rhythm Association

## Statistical Analysis Plan

[REDACTED]

## Statistical Analysis Plan

### 7.0 APPENDICES

#### APPENDIX A: CLINICAL RATIONALE FOR PRIMARY SAFETY ENDPOINT

[REDACTED]

[REDACTED]

- [REDACTED]
- [REDACTED]
- [REDACTED]

[REDACTED]

[REDACTED]

[REDACTED]	[REDACTED]	[REDACTED]	[REDACTED]
[REDACTED]	[REDACTED]	[REDACTED]	[REDACTED]
[REDACTED]	[REDACTED]	[REDACTED]	[REDACTED]
[REDACTED]	[REDACTED]	[REDACTED]	[REDACTED]
[REDACTED]	[REDACTED]	[REDACTED]	[REDACTED]
[REDACTED]	[REDACTED]	[REDACTED]	[REDACTED]
[REDACTED]	[REDACTED]	[REDACTED]	[REDACTED]
[REDACTED]	[REDACTED]	[REDACTED]	[REDACTED]

